7. STATISTICAL METHODS OF ANALYSIS

7.1. General Principles

The statistical analyses will be reported using summary tables, and figures. All analyses and tabulations will be performed using SAS® Version 9.1 or later. Continuous variables will be summarized using descriptive statistics (sample size [n], mean, standard deviation [SD], minimum, median, and maximum). Categorical variables will be tabulated with number and percentage of subjects. Unless otherwise noted, percentages will be based on the number of subjects in the treatment group within the population.

Individual subject data will be provided in listings. All listings will be sorted by treatment, site, subject and, if applicable, collection date and time.

Unless otherwise stated summaries will present data across all sites (overall).

On all figures, the comparator treatment will be represented in black with solid lines and filled squares; EXPAREL will be represented in red with solid lines and dots.

Plots of the NRS scores will show both observed and imputed scores. A change in color and line type will differentiate the imputed NRS scores. Imputed values will be represented by blue and green symbols and dashed lines for comparator and EXPAREL respectively. NRS scores obtained immediately prior to rescue will be indicated by a change in symbol. For comparator the symbol should be a triangle, for EXPAREL the symbol is a star. The following table shows the SAS symbol statements:

| Treatment | NRS Score | SAS Statement |
|------------|-----------|--|
| Comparator | Observed | symbol font=marker interpol=j line=1 value=U color=black |
| | Imputed | symbol font=marker interpol=j line=3 value=C color=blue |
| EXPAREL | Observed | symbol font=marker interpol=j line=1 value=W color=red |
| | Imputed | symbol font=marker interpol=j line=3 value=V color=green |

Note the symbol statement number will be dependent on the sort order of the treatment and NRS score group indicator variables.

Sites with fewer than 5 subjects per treatment arm will be pooled with other sites for analysis. Sites will be pooled with other small sites based on the US Census Bureau geographic regions (see [Table 1](#)). Sites meeting the criteria for pooling will be pooled with other similar sites within their census division. If the resulting pooled site within a division still doesn't have enough subjects per treatment group, it will be pooled with the site within the division with the smallest enrollment that doesn't meet the pooling criteria. If all sites within a division are pooled and the resulting pooled site still meeting the pooling criteria, the site will be pooled with other small sites within the region. The pooled site with the region still meets the pooling criteria it will be pooled with the site with the smallest enrollment from the neighboring regions.

Table 1: US Census Regions and Divisions

| Region | Division | State |
|-----------|--------------------|---|
| Midwest | East North Central | Illinois, Indiana, Michigan, Ohio, Wisconsin |
| | West North Central | Iowa, Kansas, Minnesota, Missouri, Nebraska, North Dakota, South Dakota |
| Northeast | Middle Atlantic | New Jersey, New York, Pennsylvania |
| | New England | Connecticut, Maine, Massachusetts, New Hampshire, Rhode Island, Vermont |
| South | East South Central | Alabama, Kentucky, Mississippi, Tennessee |

Table 1: US Census Regions and Divisions

| Region | Division | State |
|--------|--------------------|---|
| | South Atlantic | Delaware, District of Columbia, Florida, Georgia, Maryland, North Carolina, South Carolina, Virginia, West Virginia |
| | West South Central | Arkansas, Louisiana, Oklahoma, Texas |
| West | Mountain | Arizona, Colorado, Idaho, Montana, Nevada, New Mexico, Utah, Wyoming |

Subjects who use opioid rescue medication will have the pain scores obtained after rescue replaced using pain scores obtained prior to rescue medication use. Pain scores obtained during the window when the opioid medication is effect will be replaced. For this study the prescribed opioid rescue medication is oxycodone. The duration of effect for various opioid are listed in [Table 2](#).

Table 2: Opioid Windows

| Medication | Route | Window Used to Impute NRS |
|---------------|-------|---------------------------|
| Oxycodone | PO | 6 hours |
| Morphine | IV | 4 hours |
| Hydromorphone | IV | 2 hours |
| Hydromorphone | PO | 4 hours |
| Hydrocodone | PO | 6 hours |

PO = oral; IV = intravenous

If other rescue medications are given then the window will be determined post-hoc. If a combination opioid product is given then the window will be determined by the opioid part of the medication. Opioids given postsurgically with an indication like ‘anesthesia maintenance’ will not be included for imputation purposes.

7.1.1. Handling Missing Values

7.1.1.1. Area Under the NRS-Time Curve

7.1.1.1.1. Multiple Imputation Method

Rubin’s (1987)⁴ multiple imputation procedure will be applied to replace each missing value with a set of plausible values that represent the uncertainty about the right value to impute. This multiple imputation method is being implemented per the advice provided in “the prevention and treatment of missing data in clinical trials”⁵ For calculation of area under the curve (AUC) of NRS pain intensity scores, the windowed worst observation carried forward (wWOCF) multiple imputation procedure will be used in the following order:

- Windowed worst observation carried forward (wWOCF) for rescue medications.

For subjects who take a rescue medication, their NRS scores recorded within the window of controlled type of rescue medication (see [Table 2](#)) will be replaced by the ‘worst’ observation. The worst observation will be the highest score from time 0.25 or end of previous rescue window, to

pain score immediately prior to rescue medication for those subjects with pain score prior to each rescue medication (Amendment 2) or, for those subjects with pain scores only prior to first rescue medication use (Amendment 1) in the time interval from time 0.25 to up to the time of rescue medication. The NRS score at rescue will be included in this

calculation. Note that NRS scores in the window that are higher than the worst value prior to rescue medication will not be overwritten.

- b) After the wWOCF imputation, described in Step a, subject data still missing with a non-monotone missing pattern (ie, all pain scores between the last non-missing score and last timepoint) will have missing scores imputed using the Markov-Chain Monte-Carlo (MCMC) method (Schafer 1997)⁶, which will be applied in the multiple imputation procedure for arbitrary missing patterns. This MCMC method will use 1000 imputation datasets with NBITER=2000 and NITER=1000.
- c) The resulting data from Step b will then have the remaining monotone missing patterns, hence a parametric regression method on pain (Rubin 1987) that assumes multivariate normality will be applied for this multiple imputation procedure.
- d) The AUC and SPIS at various time intervals will be derived from the imputed NRS scores resulting from Step c.
- e) The endpoints derived in Step d will be analyzed as described in Section 7.6.2.1 for each imputation.
- f) Rubin's (1987) synthesizing procedure for the multiple imputed data will be applied to synthesize analysis results for each imputation. SAS PROC MIANALYZE will be used for this procedure. The mean parameter estimates, the asymptotic variance for this mean from the imputed data analysis in Step e will be created based on Rubin and Schenker method (1986)⁷.

For summary statistics based on multiple imputations, the mean value from each imputation will be derived for each subject. These mean values will then be summarized to obtain the summary statistics for reporting.

SAS pseudo-code for multiple imputations is provided in Section 12

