6. ANALYSIS SETS

Safety Analysis Set

The safety analysis set will include all subjects who receive study drug and will be based on the actual treatment received.

Efficacy Analysis Sets

Under the protocol, the efficacy analysis set will include all subjects in the safety analysis set who undergo the planned surgery and will be based on the randomized treatment, regardless of actual treatment received. However Amendment 2 changee the pain score collection around rescue medication use, thus subjects enrolled under Amendment 1 and Amendment 2 have differences in efficacy data collection. Subjects enrolled under Amendment 1 collected pain scores only before the first use of rescue medication while those enrolled under Amendment 2 collected pain scores prior to each use of rescue medication. This has direct impact on the derivation of the primary efficacy endpoint. Under Amendment 2 the sample size was increased to accommodate the FDA request of at least 100 subjects on EXPAREL and to ensure an adequate number of subjects in both treatment groups to enable an efficacy analyses based solely on those subjects enrolled under Amendment 2. Thus two efficacy analysis sets are defined for this study, primary and secondary efficacy analysis sets.

The primary efficacy analysis set will include all subjects enrolled under Amendment 2 in the safety analysis set who undergo the planned surgery. This will be the analysis set used for the decision on efficacy.

The secondary efficacy analysis set will include all subjects enrolled under either amendment in the safety analysis set who undergo the planned surgery. This analyses set will be used for a sensitivity analysis to ensure that the protocol amendment did not change the efficacy results. When adjusting pain scores for rescue medication use, subjects enrolled under Amendment 1 will use the highest score prior to the first rescue medication request to impute pain scores obtained in the rescue medication window.

In both efficacy analyses sets subjects will be analyzed as randomized, regardless of treatment received.

Pharmacokinetic Analysis Set

The PK analysis set will include all subjects in the safety analysis set who receive EXPAREL, provide sufficient samples to allow for calculation of PK parameters required for analysis, and do not have significant protocol deviations that may invalidate or bias the results.

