A mixed model repeated measures analysis will be performed using only the data imputed using wWOCF but not imputing any missing values outside of the rescue medication windows. The MMRM model will have fixed effects for treatment and time. The initial model will be fit with the treatment-by-time interaction. If this interaction is not significant (p-value > 0.05) the final model will include the main effects only. If the interaction is significant (p-value ≤ 0.05) the interaction will be investigated to determine if it is qualitative or quantitative. If the interaction is quantitative, the final model will include the interaction term. If the interaction is qualitative, additional analyses may be required. The treatment effect at 48 hours will be estimated from the final model.

Tipping Point

A tipping point analysis will be performed using similar imputation technique as the primary AUC calculations (see section [7.1.1.1.1](#)) but adding shift values to the imputation until the primary analysis results change direction (SAS pseudo-code below).

```
PROC MI DATA=OUTDATA_STEPB OUT=OUTDATA_TIP;
  BY _IMPUTATION_;
  CLASS TREATMENT;
  MONOTONE REG(T1 = TREATMENT / DETAILS);
  MONOTONE REG(T2 = TREATMENT T1 / DETAILS);
  ...
  MONOTONE REG(T(n-1) = TREATMENT T1 T2 T3 ... T(n-2) / DETAILS);

  MNAR ADJUST(T1 / SHIFT=Q ADJUSTOBS=(TREATMENT='EXPAREL'));
  MNAR ADJUST(T2 / SHIFT=Q ADJUSTOBS=(TREATMENT='EXPAREL'));
  ...
  MNAR ADJUST(T(n-1) / SHIFT=Q ADJUSTOBS=(TREATMENT='EXPAREL'));
  MNAR ADJUST(Tn / SHIFT=Q ADJUSTOBS=(TREATMENT='EXPAREL'));

  VAR TREATMENT T1 T2 T3 ... Tn
RUN;
```

where Q is the value to shift the results.

If the result from the primary efficacy analysis is statistically significant, the above code will be run iteratively for integer values of Q from 1 to 10 analyzing each step of the way until the result “tips” from statistically significant to not statistically significant. If the primary efficacy analysis result is not statistically significant, the above code will be run iteratively for integer values from -1 to -10 until the result “tips” from not clinically significant to clinically significant. The value of Q that results in the change in significance will be reported along with the analysis results.

Original Imputation Method

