| Complete PoSSe scale questionnaire | | | | | | | | | | | | | | | | | | | | | | X | | X | | |
| Collect scheduled PK blood sample | | | X ² | X | X | X | X | X | | X | X | X | X | X | X | X | X | X | X | X | X | X | X | X | | |
| Document any unscheduled phone calls or office visits related to pain after hospital discharge | | | | | | | | | | | | | | | | | | | | | | | X | X | X | |
| Phone call | | | | | | | | | | | | | | | | | | | | | | | | | | X |
| Record concomitant medications | | | ← | — | — | — | — | — | — | — | — | — | — | — | — | — | — | — | — | — | — | — | — | — | — | |
| Record AEs (starting at signing of ICF) ⁶ | | | ← | — | — | — | — | — | — | — | — | — | — | — | — | — | — | — | — | — | — | — | — | — | — | |

Abbreviations: AE = adverse event; ICF = informed consent form; NRS = numeric rating scale; PK = pharmacokinetic; PoSSe = postoperative symptom severity.

* Postsurgical efficacy assessments will be conducted at the timepoints specified *after the beginning of study drug administration*. At timepoints when multiple assessments coincide, the NRS pain intensity assessment will be conducted first, if applicable.

¹ Or on Day 1 prior to surgery.

² Prior to surgery.

³ Vital signs (heart rate and blood pressure) will be measured after subject has rested in a supine position.

⁴ NRS pain intensity scores also will be recorded immediately prior to each administration of rescue pain medication through 96 hours.

⁵ Subjects should only receive opioid rescue medication (oral oxycodone 5-10 mg) upon request for breakthrough pain, as needed (maximum of every 4 hours). During the 96-hour observation period, no other analgesic agents, including nonsteroidal anti-inflammatory drugs (NSAIDs), are allowed. After 96 hours, the analgesic regimen may be adjusted.

⁶ If a cardiac event (e.g., myocardial depression, decreased cardiac output, heart block, hypotension, bradycardia, ventricular arrhythmia, or cardiac arrest) or neurological event (e.g., persistent anesthesia, paresthesia, weakness, or paralysis) occurs during the study, an unscheduled PK blood sample should be obtained and, for cardiac events, an ECG should be conducted within 2 hours of the time that the event is noted. If there is a scheduled PK blood draw and ECG within 2 hours before or after the event, an additional PK blood draw and ECG are not needed.

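### Does the rescue-imputation rule break down when oxycodone doses are 4 to under 6 hours apart?

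*SAP*

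**What the plan says.** SAP 7.1.1.1.1, step a, defines the carried value: "The worst observation will be the highest score from time 0.25 or end of previous rescue window, to" the score taken just before the rescue dose, for subjects who have a score before each dose. It adds: "The NRS score at rescue will be included in this" calculation. In-window scores above the worst value are kept.

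SAP 7.1 gives the general principle: "Pain scores obtained during the window when the opioid medication is effect will be replaced". Its Table 2 sets the window: "Oxycodone | PO | 6 hours". Footnote 5 of the SAP Section 10 schedule allows rescue "upon request for breakthrough pain, as needed (maximum of every 4 hours"), as does Protocol 11.1.

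SAP Section 6 explains why the look-back restarts at each dose: "those enrolled under Amendment 2 collected pain scores prior to each use of rescue medication". Amendment 2 subjects form the primary efficacy set, so this branch governs the primary analysis.

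On sensitivity analyses, SAP 7.6.2.1 says: "A mixed model repeated measures analysis will be performed using only the data imputed using wWOCF", and "A tipping point analysis will be performed using similar imputation technique as the primary AUC calculations".

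**The concern.** A repeat dose 4 to under 6 hours after the last one falls inside the previous window. The look-back then starts later than it ends. Two readings suggest themselves.

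- **Literal:** the pre-dose score is included by name, so it alone is carried.
- **Carry-through:** the pre-dose score lies in the earlier window, so it is itself replaced first, and the earlier worst value continues.

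A scheduled score lying in both windows also has two candidate values and no stated precedence. Two programmers could therefore derive different primary AUCs from the same data. The mixed model and the tipping-point analysis both start from the same step, so neither would show it. The example code in SAP Section 12 begins after the step has been applied. The historical single-imputation analysis looks back only from the first rescue dose and also changes the missing-data method, so a different result there could not be traced to this rule.

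**Working it through.** **Scale (SAP Section 8).** With 50 per group and SD 100, the standard error is 100 × √(2/50) = 20. Then 66/20 = 3.3 and power is about Φ(3.3 − 1.96) = 0.91 (0.904 by noncentral t). The stated 90% is reproduced, and 66 NRS-hours is the yardstick.

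**Where the look-back inverts.** Window 6 h (Table 2), minimum gap 4 h (schedule footnote 5). For a gap g, start minus end = 6 − g: 2 h at g = 4, 1 h at 5, 0.5 h at 5.5, 0 at 6.

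**One subject, all scores assumed.** NRS is 2, 3, 5, 7 at 0.25, 0.5, 1, 2 h and 4 at every later time. The pre-dose score is 9 for a dose at 2.5 h and 5 for a dose at 7 h. The windows are 2.5–8.5 h and 7–13 h. Only scheduled scores are taken as AUC points (an assumption).

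Trapezoid weights at 0.25, 0.5, 1, 2, 4, 6, 8, 12, 24, 48 h are 0.125, 0.375, 0.75, 1.5, 2, 2, 3, 8, 18, 12 (sum 47.75). The first four times contribute 0.25 + 1.125 + 3.75 + 10.5 = 15.625 under every rule. The last two contribute 4 × 30 = 120.

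| Rule | Scores at 4, 6, 8, 12 h | AUC(0.25-48) |
|---|---|---|
| No rescue adjustment | 4, 4, 4, 4 | 15.625 + 60 + 120 = 195.625 |
| Literal, later window prevails | 9, 9, 5, 5 | 15.625 + 36 + 55 + 120 = 226.625 |
| Literal, higher value prevails | 9, 9, 9, 5 | 15.625 + 63 + 40 + 120 = 238.625 |
| Earlier worst carried through | 9, 9, 9, 9 | 15.625 + 135 + 120 = 270.625 |

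Carry-through exceeds the literal rule by (9 − 5) × 8 = 32 if the higher value prevails at 8 h, and by 32 + (9 − 5) × 3 = 44 if the later window prevails.

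**When nothing changes.** The difference is zero in three cases:
- the gap is 6 h or more;
- the second pre-dose score is at least the earlier worst score (9 here);
- no scheduled score falls in the second window. For a single pair of doses this holds when the second dose falls between 12 and 18 h or between 24 and 42 h, which is 6 + 18 = 24 of the 48 hours.

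With a second pre-dose score of 8, 7, 6, 5, or 4 and below, the 32 becomes 8, 16, 24, 32 or 40.

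**Trial level.** Shift in the treatment difference = per-subject difference × between-arm difference in the share affected. The documents give no shares. Assuming 5 to 30 percentage points: 32 × 0.05 = 1.6 and 32 × 0.30 = 9.6, or 2.4% to 14.5% of 66. With 44 instead of 32 the range is 2.2 to 13.2. Equal shares and equal sizes give no shift.

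**The obvious replacement rule.** One could join overlapping windows and carry the highest score so far. In the example this gives 270.6 at a 5.9 h gap and 238.6 at 6.0 h, a 32-unit step. With doses every 4.5 h from 2.5 h through 48 h and 5 before each later dose, it gives 15.625 + 9 × 45 = 420.6. The literal rule (higher value prevailing) gives 15.625 + 63 + 5 × 38 = 268.6. A single early 9 would then fill the rest of the 48 hours.

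**The case for a change.** The strongest case is that a primary-endpoint derivation should have only one answer, and here the overlap can arise within the permitted dosing interval, without any deviation. The general sentence in 7.1 can be read to overwrite the pre-dose score. Even the literal reading leaves a score in two windows unsettled. For a subject in an unbroken chain of doses the readings differ by 420.6 − 268.6 = 152, far more than 32.

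Part of this stands: the SAP states no overlap convention and no precedence. The rest is weaker. Step a is the specific rule. It names the pre-dose score as the look-back's end and includes it, whereas carry-through uses a general sentence to discard a score that Amendment 2 was written to collect. The footnote to Listing 16.2-6.1 says rescue scores are not imputed. It is attached to the multiple-imputation average column, so it is not conclusive, but it points the same way. The chain example also shows why carry-through is contestable: it lets one early score dominate, much as the protocol's first-rescue rule does.

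**Conclusion.** No change to the plan follows. The missing sentence is a detail that analysts can fill sensibly before unblinding: carry the pre-dose score, as step a says, and record in the derivation specification which value holds for a score in two windows. The rule applies equally to both arms, and neither the direction nor the size of any effect on the treatment difference can be shown from the documents. For single pairs of close doses, an assumed imbalance of 5 to 30 percentage points gives 1.6 to 9.6 NRS-hours against 66. Long chains would give more, at a frequency the documents do not report.

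Replacing the rule with joined windows would be a trade-off, not a correction. It would demote the literal rule, let early scores persist and create a step at 6 hours, and reasonable statisticians would disagree about it.

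The figures rest on assumed scores, scheduled-only AUC points and assumed shares. Section 2 of the SAP addendum was not available, so whether it addresses overlap could not be checked.

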7.6.2.3. Tertiary Efficacy Analyses

Tertiary endpoints will be summarized as appropriate (eg, descriptive statistics or tabulations). No statistical tests will be performed on these endpoints.

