 NRS = numeric rating scale at rest, where 0 = no pain and 10 = worst possible pain;
 Summary statistics based on the subject mean AUC from the multiple imputations;
 wWOCF + LOCF = imputation using the worst observation prior to use of rescue medication within a medication window and last-observation-carried-forward for missing values.
 [1] From an ANOVA with main effects of treatment and site.

Source: list SAS datasets used to create table
 SAS X.Y

DDMONYYYYTHH:MM
 program_name

Note to programmer: The raw SAS outputs from the procedures used to produce ALL 14.2-1.1 & 14.2-1.2 series tables should be saved as a possible appendix to the clinical study report (CSR). Use this template for the following tables:

Table 14.2-1.1.2: Sensitivity Analysis of AUC of NRS Pain Intensity Scores through 48 hours - Secondary Efficacy Analysis Set - Multiple Imputation Results

Table 14.2-1.1.3: Sensitivity Analysis of AUC of NRS Pain Intensity Scores through 48 hours - Primary Efficacy Analysis Set - Mixed Model Repeated Measures Results

| Pacira Pharmaceuticals | | (Page X of Y) | | Protocol: 402-C-329 |
|--|--|----------------|----------------|---------------------|
| Table 14.2-1.1.4: Sensitivity Analysis of AUC of NRS Pain Intensity Scores through 48 hours - Primary Efficacy Analysis Set - Tipping Point Analysis - Multiple Imputation Results | | Statistic | | |
| | | EXPAREL [N=XX] | Placebo [N=XX] | EXPAREL - Placebo |
| N | | xx | xx | |
| Mean | | xxx.x | xxx.x | |
| Standard Deviation | | xxx.xx | xxx.xx | |
| Median | | xxx.x | xxx.x | |
| Minimum | | xx | xx | |
| Maximum | | xxx | xxx | |
| Least squares mean [1] | | xxx.x | xxx.x | xxx.x |
| Least squares standard error of mean [1] | | xxx.xx | xxx.xx | xxx.xx |
| 95% confidence interval for treatment difference [1] | | | | (xxx.x, xxx.x) |
| p-value for treatment difference[1] | | | | 0.xxxx |
| Tipping Point [2] | | | | xx |

Note: AUC = area under the curve calculated using the trapezoidal method;
 NRS = numeric rating scale at rest, where 0 = no pain and 10 = worst possible pain;
 Summary statistics based on the subject mean AUC from the multiple imputations;
 wWOCF + LOCF = imputation using the worst observation prior to use of rescue medication within a medication window and last-observation-carried-forward for missing values.

[1] From an ANOVA with main effects of treatment and site.

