12. MULTIPLE IMPUTATION EXAMPLE PROGRAM CODE

** Note: INPUT_DATA is the dataset that contains the NRS data with the wWOOF imputation performed for the rescue pain scores **;

** Step 1 use Markov-Chain Monte-Carlo (MCMC) method to create a monotonic missing pattern **;

** Note the value for the random seed should be fixed so that the results are reproducible **;

PROC MI DATA=INPUT_DATA SEED=M NIMPUTE=1000 OUT=OUTPUT_STEP1;

 BY TREATMENT;

 MCMC IMPUTE=MONOTONE NBITER=2000 NITER=1000;

 VAR TIME_POINT_LIST;

RUN;

** Step 2 – use regression on output dataset from Step 1 to impute missing values **;

** T_i is the variable containing the pain score from time i **;

PROC MI DATA=OUTPUT_STEP1 OUT=OUTPUT_STEP2;

 BY _IMPUTATION_;

 CLASS TREATMENT;

 MONOTONE REG(T_1 = TREATMENT / DETAILS);

 MONOTONE REG(T_2 = TREATMENT T_1 / DETAILS);

...

 MONOTONE REG($T_{(n-1)}$ = TREATMENT $T_1 T_2 T_3 \dots T_{(n-2)}$ / DETAILS);

 MONOTONE REG(T_n = TREATMENT $T_1 T_2 T_3 \dots T_{(n-1)}$ / DETAILS);

 VAR TREATMENT $T_1 T_2 T_3 \dots T_n$

RUN;

** Dataset OUTPUT_STEP2 is as an ADaM dataset, include in DEFINE.XML and transfers **;

** Step 3 derive endpoint using appropriate techniques by variable _imputation_ **;

** Endpoints are: AUC(0.25-48), AUC(0.25-24), AUC(0.25-72), SPI(0.25-24), SPI(0.25-48), **;

** SPI(0.25-72) and integrated rank assessment at 24, 48 and 72 hours **;

** Step 4 get summary statistics **;

** Summary step 4a get the mean of all imputation endpoint values for each subject **;

PROC SUMMARY DATA=OUTPUT_STEP2;

 BY TREATMENT USUBJID;

 VAR ENDPOINT_VARIABLE;

 OUTPUT OUT=SUMMARYSTATSA MEAN=ENDPOINTMEAN;

RUN;

** Dataset SUMMARYSTATSA is as an ADaM dataset, include in DEFINE.XML and transfers **;

** SUMMARYSTATSA also source for a data listing **;

** Summary step 4b use subject imputation means to derive summary statistics **;

PROC SUMMARY DATA=SUMMARYSTATSA;

 BY TREATMENT;

[figure not shown]
 VAR ENDPOINTMEAN;

 OUTPUT OUT=SUMMARYSTATSB N=N MEAN=MEAN STDDEV=STDDEV MEDIAN=MEDIAN
 MIN=MIN MAX=MAX;

RUN;

```
*** Step 5 analyze imputations **;  
ODS OUTPUT ESTIMATES=MIXEDSTATSA;  
PROC MIXED DATA= OUTPUT_STEP2 METHOD=TYPE3;  
    BY _IMPUTATION_;  
    CLASS TREATMENT SITE;  
    MODEL ENDPOINT_VARIABLE = TREATMENT SITE;  
    ESTIMATE 'EXPAREL - PLACEBO' TREATMENT 1 -1;  
RUN;  
  
ODS OUTPUT PARAMETERESTIMATES=MIXEDSTATSB;  
PROC MIANALYZE DATA= MIXEDSTATSA ALPHA=0.05 THETA0=0;  
    MODELEFFECTS ESTIMATE;  
    STDERR STDERR;  

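### Descriptive SDs are taken from each subject's average over 1000 imputations, so they are too small wherever a summary contains scores filled by MCMC or regression imputation

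*SAP*

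**What the plan says.** SAP 7.1.1.1.1 sets the number of imputations: "This MCMC method will use 1000 imputation datasets with NBITER=2000 and NITER=1000". A regression step then fills the remaining monotone gaps. For inference, the endpoint is analysed in each imputed data set and the results are combined: "SAS PROC MIANALYZE will be used for this procedure".

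Descriptive statistics follow another route. SAP 7.1.1.1.1 says: "For summary statistics based on multiple imputations, the mean value from each imputation will be derived for each subject". It continues: "These mean values will then be summarized to obtain the summary statistics for reporting". The code in SAP Section 12 removes any doubt about the meaning. The comment on the first part of Step 4 reads "Summary step 4a get the mean of all imputation endpoint values for each subject", and the next reads "Summary step 4b use subject imputation means to derive summary statistics". That second call outputs N, mean, SD, median, minimum and maximum of the subject averages.

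The footnote to the Table 14.2-1.1.1 shell repeats the rule: "Summary statistics based on the subject mean AUC from the multiple imputations". Equivalent footnotes stand under the shells for Tables 14.2-1.3, 14.2-4, 14.2-6.1, 14.2-7.1 and 14.2-7.2.

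SAP 7.6.2.3.1 to 7.6.2.3.4 ask for n, mean, SD, median, minimum and maximum of the tertiary AUC, SPIS and NRS endpoints from multiply imputed data. SAP 7.6.2.3 adds: "No statistical tests will be performed on these endpoints". SAP 7.6.2.3.3 also plans plots of the mean with SD bars. SAP 11.3 lists one with imputation (Figure 14.2-1.1) and one without (Figure 14.2-1.2).

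**The concern.** Multiple imputation gives each missing score a spread of plausible values. Averaging 1000 draws for a subject replaces that spread by something close to a single predicted value. The SD across such averages is essentially the one obtained from filling each gap once with its regression prediction, a method known to understate variability. N still counts imputed subjects as if they had been observed.

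Three uses of the numbers are exposed:
- A reader of a tertiary table, where no standard error or interval is given, may divide the SD by the square root of N and get a standard error that is too small.
- The bars in Figure 14.2-1.1 will be too short if they are drawn from the same averages.
- The SDs may be used to plan later trials. This is realistic, because SAP Section 8 itself plans from SDs of earlier studies.

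**Working it through.** **Direction.** Write subject i's value in imputation m as a_i + d_im, where a_i is the subject's average and the d_im average to zero over m. The cross-product terms cancel when averaged over m, so

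average within-imputation variance = variance of the a_i + average over m of the variance of d_im across subjects.

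The last term cannot be negative. It is zero when nothing is multiply imputed. The SD of the averages can therefore never exceed the root of the average within-imputation variance. The mean is unchanged.

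**Size.** Let f be the share of subjects whose endpoint is imputed and u the share of its variance that their observed scores do not explain. If imputed and observed subjects are otherwise alike,

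variance of averages = s²(1 - f) + f(1 - u)s² = s²(1 - f·u), so SD ratio = √(1 - f·u).

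The documents give neither f nor u. Assumed values:
- f = 5%, u = 0.3: √0.985 = 0.9925, or 0.8% too small.
- f = 10%, u = 0.5: √0.95 = 0.9747, or 2.5% too small. A true SD of 100 is shown as 97.5 and one of 128 as 124.8 (100 to 128 is the range in SAP Section 8).
- f = 20%, u = 0.7: √0.86 = 0.9274, or 7.3% too small.
- Extreme, f = 30%, u = 1: √0.70 = 0.837, or 16.3% too small.
- f = 0: ratio 1, no error.

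**Simulation.** 100 subjects, NRS at the scheduled times from 0.25 to 48 hours, SD 2.5, correlation 0.8 between adjacent times, 1000 imputations and 20 replicates. The last one, two or four scores were missing in a share of subjects. The table gives the SD understatement, from one to four missing scores:

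| Subjects with missing scores | AUC(0.25-48) | NRS at 48 h |
|---|---|---|
| 5% | 0.1% to 1.5% | 1.0% to 2.3% |
| 10% | 0.2% to 2.5% | 1.7% to 3.7% |
| 20% | 0.3% to 5.4% | 3.5% to 8.2% |

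A cross-check with only the 48-hour score missing: u = 1 - 0.8² = 0.36, so the formula gives 0.9%, 1.8% and 3.7% at 5%, 10% and 20%. The simulation gave 1.0%, 1.7% and 3.5%. A separate simulation with rescue-adjusted scores, missing at 24 and 48 hours, gave SD ratios for AUC(0.25-48) of 0.997 (5% missing) and 0.994 (10%).

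**Link to planning.** The plan states no figure for this effect. Its power statement reproduces: with 50 per group and two-sided 0.05, the t-test has 90.4% power for a difference of 66 with SD 100, and 90.6% for 86 with SD 130. Required sample size goes with the square of the SD, so a later trial planned from an averaged SD would be short by the fraction f·u. That is 0.05 × 0.3 = 1.5% to 0.20 × 0.7 = 14% over the assumed range.

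**The case against.** The strongest defence is that nothing is decided on these SDs. The primary and secondary AUC comparisons are run per imputation and pooled by Rubin's rules, and their tables show a standard error, interval and p-value beside the SD. The tertiary endpoints are descriptive by design. The footnotes disclose that the statistics rest on subject means. Listing 16.2-6.1 sets observed scores beside averaged ones. Table 14.2-1.1.5 gives AUC(0.25-48) under the historical single imputation as a bridge to older studies. Protocol 13.1 keeps subjects in the facility for 96 hours, so missing scores may be few.

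All of this stands and limits the importance. It does not make the SD right. A footnote does not tell a reader that the SD is biased or by how much. The single-imputation table covers only AUC(0.25-48), and no unimputed version of the AUC or SPIS summaries is planned.

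Three stronger readings are tempting but not supported:
- A reader might infer that every SD for these endpoints is too small. Only scores filled by MCMC or regression vary across imputations. The wWOCF replacements are the same in all 1000 data sets, and an arm or time point with no missing score has the correct SD.
- A reader might infer that the SD is the only measure of spread for the tertiary endpoints. Minimum and maximum are also reported, although from the same averages. What is absent is a standard error or interval.
- A reader might infer that all the mean plots, or the treatment test, are affected. Figure 14.2-1.2 uses no imputation, and the test does not use these SDs.

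**Conclusion.** The point holds as a minor reporting fault. The direction follows from algebra and needs no assumption: wherever scores are multiply imputed, the SD from subject averages is too small. This reaches Tables 14.2-1.1.1, 14.2-1.3, 14.2-4, 14.2-6.1, 14.2-7.1 and 14.2-7.2, the 24- and 72-hour tables built on the same shells, and Figure 14.2-1.1 if it is drawn from the same averages.

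The size rests on a missing-data rate and a predictability that the documents do not give. The assumed range gives 0.8% to 7.3%. With 5% to 10% missing, an error of about 0.1% to 2.5% for AUC(0.25-48) is more likely, and it is larger for single late NRS scores. The efficacy conclusion does not change.

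**What to change.** In SAP 7.1.1.1.1 and Step 4 of the Section 12 code, compute the statistics by treatment within each imputed data set, then combine them:
- report the average of the means and of the medians;
- report the square root of the average within-imputation variance as the SD;
- take minimum and maximum from observed values (after wWOCF adjustment), or label them as subject-averaged;
- show in each table the number of subjects with any multiply imputed score;
- draw Figure 14.2-1.1 from the same results, and amend the footnotes to match.

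The count of imputed subjects matters even with the corrected SD, because SD/√N still leaves out the between-imputation part of the standard error. The cost is a few lines of code and slightly larger SDs. The means and the pooled inference do not change.
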